#### **Informed Consent**

Subjects will sign and date a study specific, Independent Ethics Committee (IEC)/Independent Review Board (IRB) approved, informed consent form before any study procedures are performed on the subject in order to participate in this study. Details regarding how informed consent will be obtained and documented are provided in [Section 9.3](#). Written consent will be required for a subject in order to participate in the optional vaccine sub-study ([Appendix O](#)).

#### **Inclusion/Exclusion Criteria**

Subjects will be evaluated to ensure they meet all inclusion criteria and have none of the exclusion criteria at the Baseline/Week 0 visit.

#### **Patient's Global Assessment of Disease Activity Visual Analog Scale (VAS)**

At visits specified in [Table 2](#), the subject will rate the severity of the RA symptoms within the last 24 hours and how he/she is doing from 0 to 100 using the Visual Analog Scale, which consists of a horizontal 100 mm line anchored at either end by opposite adjectives reflecting the spectrum/severity of the parameters assessed. This assessment will be used for the DAS28 [CRP] calculation in this study ([Appendix E](#)).

Due to a state of emergency or pandemic situation like COVID-19, subject visits may be conducted via phone or video conference. In these situations, the Patient's Global

Assessment of Disease Activity will be completed by the physician at the next feasible visit.

### **Patient's Assessment of Pain Visual Analog Scale (VAS)**

At visits specified in [Table 2](#), the subject will rate the severity of pain due to rheumatoid arthritis in the past week from 0 to 100 ([Appendix F](#)) using the Visual Analog Scale, which consists of a horizontal 100 mm line anchored at either end by opposite adjectives reflecting the spectrum/severity of the parameters assessed.

The subject should complete the VAS before site personnel perform any clinical assessments and before any interaction with site personnel has occurred to avoid biasing the subject's response.

Due to a state of emergency or pandemic situation like COVID-19, subject visits may be conducted via phone or video conference. In these situations, the Patient's Assessment of Pain will be completed by the physician at the next feasible visit.

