## **5.3 Efficacy and Safety Assessments/Variables**

### **5.3.1 Efficacy and Safety Measurements Assessed and Flow Chart**

Study procedures will be performed as summarized in [Table 2](#). All subjects must meet the study selection criteria outlined in Section [5.2.1](#) and Section [5.2.2](#) in order to be eligible for the study.

Study visits may be impacted by state of emergency or pandemic situations like COVID-19. This may include changes such as virtual visits, visits at alternative locations, or changes in the visit frequency and timing of study procedures, among others. Additional details are provided in Section [5.3.1.1](#). Every effort should be made to ensure the safety of subjects and site staff, while maintaining the integrity of the study.

Supplemental study case report forms should be completed in the event of missed/virtual visits, or study drug interruptions or discontinuations related to COVID-19.

Study Visits and/or activities should be performed as scheduled whenever possible. During a state of emergency or pandemic situation, if it is not possible for all study

procedures to be performed as specified due to travel restrictions or other reasons, the following modifications are allowed:

- If permitted by local regulations, the IRB/IEC and the subject, study visits may be conducted in a subject's home residence (see Section 5.3.1.1 – Sub-Section "Optional Home Healthcare Service Due to State of Emergency or Pandemic Situation like COVID-19").
- The following study activities may be performed virtually by phone/video conference:
  - Adverse event assessment
  - Concomitant therapy assessment including compliance to contraception requirements, if applicable
  - Latent TB risk assessment
  - Communication of in-home urine pregnancy test result
  - Dispense study drug and subject dosing diary (see Section 5.3.1.1 - Sub-Section "Study Drug Dispensing, Dosing, and Compliance" for details about the Direct-to-Patient shipment)
  - Review of subject dosing diary, compliance to IP administrations
- During a virtual visit, the following activities should not be performed:
  - Patient Questionnaires including Patient's Global Assessment of Disease Activity and Patient's Assessment of Pain
  - Vital Signs and Body Weight
  - Physical Examination
  - Physician's Global Disease Activity VAS (PhGA)
  - Tender Joint Count (TJC) 68/Swollen Joint Count (SJC)66

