### **Health Outcomes Questionnaires**

Subjects will complete the following questionnaires as specified in [Table 2](#):

- Health Assessment Questionnaire – Disability Index (HAQ-DI) to assess the physical function and health-related quality of life of each subject ([Appendix G](#))
- FACIT – Fatigue Scale ([Appendix H](#))
- Work Instability Score for Rheumatoid Arthritis (RA-WIS) ([Appendix I](#)) is only required for those subjects who are currently working at the time that the questionnaire is administered
- EuroQoL-5D (EQ-5D) ([Appendix J](#))

The subject should complete the questionnaires before site personnel perform any clinical assessments and before any interaction with site personnel has occurred to avoid biasing

the subject's response. The patient reported outcome questionnaires will only be administered to patients and analyzed where a validated translation is available in their local language.

Due to a state of emergency or pandemic situation like COVID-19, subject visits may be conducted via phone or video conference. In these situations, questionnaires will be completed by the subject at the next feasible visit.

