## Appendix E. Patient's Global Assessment of Disease Activity Example

### Visual Analog Scale (VAS)

VAS will be used to assess the subject's global assessment of disease activity. Each VAS consists of a horizontal 100 mm line anchored at either end by opposite adjectives reflecting the spectrum/severity of the parameters assessed:

- *Patient's global assessment of disease activity (within last 24 hours)*  
The subject will rate the severity of the RA symptoms and how he/she is doing from 0 to 100. This assessment will be used for the DAS28 [CRP] calculation in this study (see example below):

Please place a vertical mark on the line below to indicate how well your rheumatoid arthritis has been doing during THE LAST 24 HOURS:

0 \_\_\_\_\_ 100  
Very Well Very Poorly

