**Appendix F. Patient's Assessment of Pain Example**

**Visual Analog Scale (VAS)**

VAS will be used to the patient's assessment of pain. Each VAS consists of a horizontal 100 mm line anchored at either end by opposite adjectives reflecting the spectrum/severity of the parameters assessed:

How much pain have you had because of your condition within the previous week?

Place a mark on the line below to indicate how severe your pain has been.

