9.4.3 Patient's Global Assessment of Disease Activity Visual Analog Scale (VAS)

The subject will assess his/her disease activity for the past 24 hours using a Patient's Global Assessment of Disease VAS. The range is 0 to 100 mm with no activity being indicated by 0 and severe activity by 100.

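### Protocol 5.3.1.1 has the physician complete two patient-rated scales after a phone or video visit, against its own definitions, the forms and the SAP

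*Protocol*

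**What the plan says.** The Patient's Global and Patient's Pain sections of Protocol 5.3.1.1 each open by making the subject the rater. The Pain section adds a safeguard against influence from staff: "The subject should complete the VAS before site personnel perform any clinical assessments".

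Each section closes with a paragraph on emergency visits held by phone or video. For the Patient's Global, the deferred rating is covered by "Assessment of Disease Activity will be completed by the physician at the next feasible visit". For Pain the text is "the Patient's Assessment of Pain will be completed by the physician at the next feasible visit".

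Protocol 5.3.1 lists what must not be done at a virtual visit and groups both scales under "Patient Questionnaires including Patient's Global Assessment of Disease Activity and Patient's Assessment of Pain". For HAQ-DI, FACIT, RA-WIS and EQ-5D, the matching emergency sentence is "In these situations, questionnaires will be completed by the subject at the next feasible visit".

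**The concern.** A patient-reported scale cannot be rated by the subject by definition and also completed by the physician when deferred. The two sentences are the scale-specific instruction on who completes a deferred assessment, so a site could act on them.

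If it did, nothing in the SAP would screen the value out. Under the As Observed rule in SAP 9.1.1 all observed data are used, and no rule refers to the rater. Patient's Global enters ACR response, DAS28(CRP), CDAI and SDAI; Pain enters ACR response. Both are also change-from-baseline endpoints in their own right (SAP Table 2). CDAI and SDAI add a patient global to a physician global that the protocol wants rated independently of the subject's own view. With a physician completing both, that distinction is lost for the visit.

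**Working it through.** The plan gives no figure to reproduce, so the first step is to compare who is named as rater.

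| Place | Patient's Global | Patient's Pain |
|---|---|---|
| Protocol 5.3.1.1, opening sentence | subject | subject |
| Protocol 5.3.1.1, Pain safeguard | not stated | subject, before contact with staff |
| Protocol 5.3.1, virtual-visit list | patient questionnaire | patient questionnaire |
| Protocol Appendices E and F | "indicate how well your rheumatoid arthritis has been doing during THE LAST 24 HOURS" | "How much pain have you had because of your condition within the previous week" |
| SAP 9.4.3 and 9.4.5 | "The subject will assess his/her disease activity for the past 24 hours using a Patient's Global Assessment of Disease VAS" | subject |
| Protocol 5.3.1.1, emergency sentence | **physician** | **physician** |

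Only the emergency sentences name the physician. Their wording matches the emergency sentence for the Physician's Global, where it is correct, so text was probably carried over. That is an inference. SAP Appendix D, on COVID-19, does not provide for a proxy rating. Protocol 10.2 says the listed device assessments are completed by subject or physician, but that list mixes both kinds of tool and authorises no substitution.

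**Weight of one rating.** Inputs are the formulas in SAP 9.4.6 to 9.4.8.

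- DAS28(CRP) contains 0.014 × Patient's Global in mm. A 10 mm difference gives 0.014 × 10 = 0.14. The gap between the remission cut of 2.6 and the low-disease-activity cut of 3.2 is 0.6, which equals 0.6 / 0.014 ≈ 43 mm.
- CDAI and SDAI contain Patient's Global in cm. A 10 mm difference is 1 cm, hence 1 point. The CDAI cuts are 2.8 and 10.

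**Where a deferred rating can be made.** Table 2 marks neither scale for unscheduled visits. The home healthcare option lists neither. Protocol 10.2 says the device takes entries only at protocol visits. The make-up therefore most likely falls at the next Table 2 visit. Footnote e puts both scales before any other procedure there, and 5.3.1.1 makes the subject the rater.

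**Cost of setting a non-subject value aside**, when the window holds no subject-entered value:

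- Without Patient's Global, DAS28(CRP), CDAI and SDAI are missing, because each needs all its components. Without Pain alone, none of them is affected.
- ACR follows the examples in SAP 9.4.1, here with both joint counts improved and all other core measures observed. At least 3 of 5 measures must improve.
  - One scale removed, k of the other 4 improved: k ≥ 3 is Yes; k ≤ 1 is No, since k + 1 < 3; k = 2 is missing (example G).
  - Both removed, k of the other 3 improved: k = 3 is Yes (example A); k = 0 is No, since 0 + 2 < 3; k = 1 or 2 is missing.

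**The case against.** The strongest reply is that this is an evident slip with little room to do harm. The forms speak to the patient, and the definitions and the SAP all point to the subject. The device limits in Protocol 10.2 also allow only one entry of a given assessment per visit. A physician's value could therefore enter at the next scheduled visit only by displacing the subject's own required rating. Windowing narrows reach further: from Week 24 the SAP windows are contiguous and 84 days wide, so a make-up at the next visit normally counts for that visit and leaves the missed one empty. Efficacy is descriptive, without tests. Nothing shows that any physician-entered value exists, or that records identify the rater.

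Most of this stands, and it limits the reach. The pieces of evidence also overlap: they largely restate that these are patient-rated scales. The four-questionnaire sentence reaches the two scales only through the label in 5.3.1, and footnote e fixes timing, not the rater. None of it removes the contradiction. The one-entry limit means that following the text would replace a patient report, which is still an error. The ACR cases above describe the cost of the check, not harm from the plan.

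**Conclusion.** The concern holds as a minor internal contradiction. Confidence is high that the two sentences conflict with the rest of the plan; that is not a claim that ratings were affected. The known size is per assessment: 0.14 in DAS28(CRP) and 1 point in CDAI and SDAI for each 10 mm of difference in Patient's Global. Neither a rater difference nor a number of affected assessments is assumed, so no shift in any reported rate or mean is claimed. Reach is limited to assessments deferred from emergency phone or video visits.

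**What to change.** In the emergency sentences of the Patient's Global and Patient's Pain sections of Protocol 5.3.1.1, change physician to subject, and send sites a notice. The cost is one word in each of two sentences, plus the notice.

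As a secondary check for data already collected, see whether source or device records identify who entered the value. Where they show that it was not the subject, do not analyse the value as a patient report, and give the count per scale and visit. The analysis cost is the missing composites set out above.

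Where the rater is not recorded, the virtual-visit count in SAP Appendix D is an upper bound for each scale separately. It covers COVID-19 virtual visits only and assumes the practice was confined to them, since missed visits and partial in-person visits are counted apart.

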### **Health Outcomes Questionnaires**

Subjects will complete the following questionnaires as specified in [Table 2](#):

- Health Assessment Questionnaire – Disability Index (HAQ-DI) to assess the physical function and health-related quality of life of each subject ([Appendix G](#))
- FACIT – Fatigue Scale ([Appendix H](#))
- Work Instability Score for Rheumatoid Arthritis (RA-WIS) ([Appendix I](#)) is only required for those subjects who are currently working at the time that the questionnaire is administered
- EuroQoL-5D (EQ-5D) ([Appendix J](#))

The subject should complete the questionnaires before site personnel perform any clinical assessments and before any interaction with site personnel has occurred to avoid biasing

the subject's response. The patient reported outcome questionnaires will only be administered to patients and analyzed where a validated translation is available in their local language.

Due to a state of emergency or pandemic situation like COVID-19, subject visits may be conducted via phone or video conference. In these situations, questionnaires will be completed by the subject at the next feasible visit.

### **Medical and Surgical History**

Any updates to the Medical and Surgical History will be obtained at the Baseline/Week 0 or at any visit during the study.

### **Vital Signs**

Vital sign determinations of systolic and diastolic blood pressure in sitting position, pulse rate, respiratory rate, and body temperature will be obtained at scheduled study visits as specified in [Table 2](#) prior to blood draws.

### **Body Weight**

Body weight will be measured at all scheduled visits as specified in [Table 2](#).

### **Physical Examination**

A complete physical examination will be performed at the designated study visits as specified in [Table 2](#). Any physical examination abnormalities assessed by the investigator at Week 0 (Day 1) after first dose of study medication in Study M13-538 should be recorded as adverse events and captured on the appropriate eCRF in Study M13-538. All findings whether related to an adverse event or part of each subject's medical history will be captured on the appropriate eCRF page. Any physical examination abnormalities assessed by the investigator prior to the first dose of study medication should be recorded in Study M13-550 or Study M13-537 RCT as appropriate, as adverse events and captured on the appropriate eCRF.

Due to a state of emergency or pandemic situation like COVID-19, subject visits may be conducted via phone or video conference. In these situations, if a visit by phone or video conference occurs at one of the designated study visits specified to complete physical examination, the complete physical examination will be performed at the next feasible visit. A symptom-directed physical examination may be performed at any visits when necessary.

### **Physician Global Assessment of Disease Activity Visual Analog Scale (VAS)**

At visits specified in [Table 2](#), the Physician will rate global assessment of subject's current disease activity ranging from 0 to 100 independent of the subject's self-assessment ([Appendix D](#)) using the Visual Analog Scale, which consists of a horizontal 100 mm line anchored at either end by opposite adjectives reflecting the spectrum/severity of the parameters assessed.

Due to a state of emergency or pandemic situation like COVID-19, subject visits may be conducted via phone or video conference. In these situations, the Physician Global Assessment of Disease Activity will be completed by the physician at the next feasible visit.

### **Tender Joint Count (TJC) and Swollen Joint Count (SJC) Assessment**

#### **Tender Joint Count (TJC)**

An assessment of 68 joints ([Appendix C](#)) will be done for tenderness by pressure manipulation on physical examination at visits specified in [Table 2](#). Joint pain/tenderness will be classified as: present ("1"), absent ("0"), replaced ("9") or no assessment ("NA").

#### **Swollen Joint Count (SJC)**

An assessment of 66 joints ([Appendix C](#)) will be done by directed physical examination at visits specified in [Table 2](#). The joints to be examined for swelling are the same as those

examined for tenderness, except the hip joints are excluded. Joint swelling will be classified as present ("1"), absent ("0"), replaced ("9") or no assessment ("NA").

If a patient receives an intra-articular injection during the study, the injected joint(s) should be scored as "NA = no assessment" for 90 days following injection.

If possible, the TJC and SJC should be performed by an independent joint assessor who should not perform any other study related procedures, as much as possible. In order to minimize variability, the same independent joint assessor should evaluate the subject at each visit for the duration of the trial. A back-up independent assessor, who is trained and competent in performing such assessments, should be identified. It is the responsibility of the Principal Investigator to ensure all assessors are qualified to perform joint assessments and that all training is documented. If the independent assessor is not available, the pre-identified back-up assessor will perform such assessments.

Due to a state of emergency or pandemic situation like COVID-19, subject visits may be conducted via phone or video conference. In these situations, the TJC and SJC will be performed at the next feasible visit by the independent joint assessor, if possible.

### **Pregnancy Test**

- For women of childbearing potential, urine pregnancy test will be performed monthly at home between scheduled study visits. The results of these tests will be verbally communicated (via telephone) to the site. If a urine pregnancy test is positive, the subject must stop dosing, come in to clinic and have blood drawn for a serum pregnancy test that will be analyzed at the central laboratory. A urine pregnancy test will be performed at all scheduled study visits as specified in [Table 2](#), on all female subjects of childbearing potential. If urine pregnancy test (which is performed at the site) is negative, begin or continue dosing. If urine pregnancy test is positive at any visit, withhold dosing and perform a serum pregnancy test for confirmation. The serum pregnancy test will be sent to and performed by the central laboratory. Pregnant subjects must be discontinued from the study. In the event a pregnancy test comes back borderline, a repeat test is required.

At each visit, the study staff should review the pregnancy avoidance recommendations with each subject of childbearing potential and male subjects with a partner of childbearing potential, and document this discussion in the subject's source records.

Female subjects who are either postmenopausal, defined as:

- Age  $\geq$  55 years with no menses for 12 or more months without an alternative medical cause; or
- Age  $<$  55 years with no menses for 12 or more months without an alternative medical cause AND an FSH level  $>$  40 IU/L.

and/or surgically sterile (bilateral oophorectomy or hysterectomy) are exempt from pregnancy testing.

In the event a urine pregnancy test may not be performed at the protocol specified visits due to study modifications related a state of emergency or pandemic situation like COVID-19, it can be performed by subjects at a local laboratory or it is possible for the Investigator to arrange a shipment from the study site directly to the subject's home of urine pregnancy test kits to have the urine pregnancy test done at home (see Section 5.3.1.1 - Sub-Section "Study Drug Dispensing, Dosing, and Compliance" for details). Home urine pregnancy test should be performed monthly, regardless of ability to obtain other laboratory samples.

If, during the course of the study, a woman becomes surgically sterile or post-menopausal and complete documentation as described as above is available, pregnancy testing will no longer be required.

A breastfeeding or pregnant female will not be eligible for participation or continuation in this study.

## **TB Testing**

For subjects with a negative QuantiFERON-TB Gold (or PPD) test at screening of the preceding RCT, an annual QuantiFERON-TB Gold (or protein purified derivative [PPD]) re-test will be required at visits indicated in [Table 2](#). All subjects will be assessed for evidence of increased risk for TB by a questionnaire ([Appendix L](#)).

Subjects with a negative QuantiFERON®-TB Gold test OR negative PPD TB skin test AND no new evidence of increased TB risk based on the questionnaire may continue in the study.

Subjects with documentation of prior positive result of QuantiFERON-TB Gold Test (or equivalent) and/or PPD are not required to repeat either test during the study and should be considered positive.

If the QuantiFERON-TB Gold test is indeterminate, the QuantiFERON-TB Gold test should be performed locally (or through the central laboratory if not locally available) to rule out a positive test result. If testing remains indeterminate or is positive, then the subject is considered to be positive for the purpose of this study. If the local testing result is negative, then the patient is considered to be negative.

- Interpretation of a positive annual TB test in low risk subjects: In cases where the QuantiFERON-TB Gold Plus test by the central laboratory is positive and the Investigator considers the subject at low risk for TB and has no clinical suspicion of TB, the Investigator may perform a local QuantiFERON-TB Gold Plus test (or repeat testing through the central laboratory if not locally available) to confirm the positive test result. If the repeat testing result is negative, the Investigator may consider the test to be negative based on his/her clinical judgment; if the repeat testing result is positive or indeterminate, the test is considered positive.
- An equivalent Interferon Gamma Release Assay (IGRA) (such as T-SPOT TB test) may be substituted for the QuantiFERON-TB Gold Plus.

If one of the annual tests has a positive test result (seroconversion), a chest x-ray (CXR) needs to be performed as soon as possible to aid in distinguishing active versus latent TB. Expert consultation can be considered per Investigator's discretion. Any positive TB screen after the patient has started the study should be reported as an adverse event (AE).

Subjects with evidence of active TB infection will be discontinued from the trial.

For subjects with seroconversion on an annual TB test, if a CXR cannot be done due to state of emergency or pandemic situation like COVID-19, the Investigator should contact the AbbVie TA MD to determine if the subject may continue on study drug. CXR should be performed as soon as restrictions allow at the study site or local hospital/facility.

If the subject is experiencing signs or symptoms suspicious for TB or something has changed in the subject's medical history to warrant a repeat test before the next scheduled annual TB re-test, the case must be discussed with the AbbVie Therapeutic Area Medical Director.

Obtain a CXR for subjects with newly identified positive PPD or QuantiFERON-TB Gold test and every 48 weeks for subjects with TB risk factors as determined by the TB risk assessment form ([Appendix H](#)) or for subjects living in areas endemic for TB. Any positive TB test result after the subject has started study drug should be reported as an adverse event (AE).

The results of the TB test(s) will be retained at the site as the original source documentation.

